International Multicenter Double-blind Placebo-Controlled Parallel-Group Randomized Clinical Trial of Efficacy and Safety of Ergoferon in the Treatment of Viral Intestinal Infections in Children

Phase IV

Sponsor OOO «NPF «MATERIA MEDICA HOLDING»

Protocol number MMH-ER-008

Version date: November 02, 2015

ClinicalTrials.gov Id: NCT03039699

Protocol Summary

This document represents the protocol summary for the study on human subjects. The study will be carried out in accordance with ICH GCP, National Standard of the Russian Federation GOST 52379-2005 "Good Clinical Practice", Helsinki Declaration of World Medical Association, relevant requirements of the regulatory authorities as well as the study procedures.

Title of Study

International multicenter double-blind placebo-controlled parallel-group randomized clinical trial of efficacy and safety of Ergoferon in the treatment of viral intestinal infections in children.

Phase: IV

Sponsor: OOO "NPF "Materia Medica Holding", Moscow, Russia

Protocol No. MMH-ER-008

Objective of the study

• To obtain additional data on the efficacy and safety of Ergoferon in the treatment of viral intestinal infections in inpatient children.

Endpoints

Primary endpoint

1. Average diarrhea duration¹.

Secondary endpoints

- 1. Percentage of patients without diarrhea following 48, 72, and 96 hours of treatment.
- 2. Percentage of patients with recovery² following 48, 72, and 96 hours of treatment.
- 3. Average illness duration (from the enrollment to the recovery).
- 4. Total CDS score at 24, 48, and 72 hours after treatment initiation.
- 5. Average vomiting duration (if any).
- 6. Percentage of patients with negative PCR tests on Days 3, 4, 6, and 10 of observation versus baseline (no RNA detection of rotaviruses/ noroviruses/ astroviruses/ adenoviruses in patients who had positive tests at baseline).
- 7. Percentage of patients with worsening of illness³ and/or hospital-acquired infection⁴.

CONFIDENTIAL Page 2 of 14

¹ Diarrhea duration is considered as the time between receiving the first dose of investigational medicine /placebo and the normal consistency of stool pattern (to the previous stool consistency before diarrhea), i.e.

¹⁾ time to the first loose stool which is followed by two normal consistency stools over 24 h (infants may have three episodes of loose stool over a 24-hour period), or 2) time to ≤3 episodes of stool occurring over 24 h, at least 2 of which are normal consistency stools, or

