⁶ The data of a patient whose PCR test indicates a bacterial etiology of acute intestinal infection will not be included in the analysis of treatment efficacy. For the sake of sufficiency of data for the efficacy analysis, it is statistically assumed that 50% of patients will test negative for viral etiology of acute intestinal infection.

pediatrician, and the examination results, including the CDS scores, will be recorded in source documents. The patient's parent/adopter will fill patient diary on a daily basis, recording the presence/absence of diarrhea signs, vomiting, and body temperature. The pediatrician will check correctness of diary filling. After discharge on day $10 \ (\pm 1)$ Visit 7 is scheduled (personal at the site/at home or distant/phone call) to interview the parents/adopters about the patient's health, presence of any complications, and use of medications (the investigator will fill out a questionnaire).

Collection of stool specimens and repeat PCR for Rotaviruses/Noroviruses/Astroviruses/Adenoviruses, Shigella spp., EIEC, Salmonella spp., and Campylobacter spp. will be performed on Days 3, 4, and 6 of inpatient observation and after discharge from the hospital (Day 10); collection of blood and urine specimens for safety tests will be carried out at baseline and before hospital discharge (day 6). The recording of the intake of study therapies and of concomitant medications as well as the assessment of compliance with and safety of the study therapies will be performed on Days 2-6 and 10.

Patients who recovered while in hospital and are discharged from the unit earlier than at 5 days will undergo the procedures of Visit 6, including the collection of biological specimens for PCR (efficacy evaluation) and biochemistry, blood test and urinalysis (safety assessment). The parents/adopters will be given the blister pack with the remaining study drug so that the patient can continue the treatment.

Inclusion and exclusion criteria

Inclusion criteria

- 1. Patients of either gender aged from 6 months to 6 years old hospitalized to infectious department.
- 2. Diarrhea (watery stool without visible abnormal foreign substances [transparent mucus is possible] ≥ 3 times a day).
- 3. Dehydration symptoms according to CDS scale ≥ 1 .
- 4. The first 48 hours from the onset of the first diarrhea episode.
- 5. Start of study treatment (Ergoferon/Placebo) within 12 hours after the start of the standard hospital therapy.

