Medical history	+						
Physical examination	+	+	+	+	+	+	
Body weight measurement	+					+	
Body length/height measurement	+						
Evaluation of dehydration symptoms using CDS	+	+	+	+	+	+	
Diary supply	+						
Checking the correctness of filling the diary		+	+	+	+	+	
Parent/adopter inquiry (personal/by phone) and filling questionnaire "Parent's/adopter's inquiry data"							+
Return of patient diary						+	
Concomitant therapy	+	+	+	+	+	+	+
Eligibility assessment	+						
Obtaining stool sample for PCR diagnosis	+		+	+		+	+*
Safety laboratory tests (hematology, serum chemistry,	+					+	

CONFIDENTIAL Page 9 of 14

urinalysis)							
Randomization and prescription of study drug	+						
Study drug supply							
, , , , , , , , , , , , , , , , , , ,	T .						
Basic medication supply	+	+	+	+	+		
Study drug accountability,						+ **	+ **
compliance assessment						Į.	!
Evaluation of treatment safety	+	+	+	+	+	+	+

^{*} All the subjects will receive sterile containers for stool storage and transportation on day 10. In case of a phone visit on day 10 stool samples will be delivered to the local laboratory by a courier.

Statistical Analyses.

Samples

Total set: all patients included in the study whose parents/adoptive parents signed the Informed Consent Form for the patient's participation in the study. All AEs including those occurred prior to the study therapy will be considered throughout the study for this sample.

Safety population: all patients who received at least one dose of the study drug. This sample will be used to *analyze the study treatment safety and tolerability*, since all the AEs identified after the study product administration will be recorded.

Full Analysis Set. This sample includes all enrolled and randomized patients, except for those who have experienced at least one of the following events:

- 1) non-compliance with inclusion / exclusion criteria;
- 2) the patient has not taken a single dose of the study drug;
- 3) lack of any data of the patient following randomization;
- 4) withdrawal of a patient due to early discharge (discharge of patient with persistent symptoms of acute intestinal infections on days 2-5 of hospitalization before the study treatment is completed at the parent's/adopter's request).

This sample is the most consistent with the "Intention-to-treat" principle, will be used for the *Intention-to-treat analysis (ITT analysis) of the the study therapy efficacy*.

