Per protocol set. This sample includes all patients who completed the therapy as per the study protocol without any missing visits or significant protocol deviations. This sample will be used for the *Per Protocol analysis (PP- analysis) of the the study therapy efficacy*.

Mean value in Placebo group for the relevant day will be used to fill lacking/missing data.

Data treatment and all statistical calculations under the protocol will be made using SAS-9.4 statistical software¹⁰.

CONFIDENTIAL Page 10 of 14

^{**} Return of the study product is made after 5-day treatment course (on Day 6). If the subject is discharged sooner than on day 6, the parent/adopter will be given a blister with the remaining product to complete outpatient therapy; in this case the product return and determination of compliance will be made on Day 10 ± 1 .

¹⁰ Holder of license: OOO "NPF "Materia Medica Holding", No. 70100045.

Evaluation of sample size

The sample size has been assessed on the basis of the following rules and assumptions:

- 1. Statistical provisions.
 - 1.1 the power of the statistical tests " $P = (1 \beta)$ " is assumed to be 80% (the probability of correct rejection of the null hypothesis is 0.8);
 - 1.2 the probability of a type I error " α " is allowed to be less than 5% (the probability of the erroneous acceptance of an alternative hypothesis is less than 0.05);
 - 1.3 the statistical criteria are 2-sided;
 - 1.4 the calculation of the sample size is based on the assumptions about the expected effects, mainly declared in the primary efficacy criterion of the Protocol;
 - 1.5 statistical null and alternative hypotheses are formulated as follows:

$$H_0: m_2-m_1 \le 0$$

$$H_1: m_2-m_1>0,$$

where $\mathbf{m_1}$ – mean disease duration in Ergoferon group,

m₂ – mean disease duration in Placebo group;

- 1.6 to assure potential adjustment of sample size or terminate the study due to inadequate efficacy/high efficacy, interim analysis will be carried out in which:
 - a. calculations will be made using O'Brien-Fleming boundary;
 - b. proportions of the subjects completing the study and yielding the results for interim and final analyses, will be taken as 0.5 and 1.0 (i.e. interim analysis will be made after recruitment of half of the planned number of the clinical study subjects.
- 1.7 therefore, sample size will be calculated taking into account
 - a. interim analysis;

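### The only missing-data rule fills gaps with the Placebo mean, with no limit by arm, endpoint or analysis set; it can distort the Full Analysis Set comparison, and unresolved diarrhea has no scoring rule

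*Combined protocol and SAP*

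**What the plan says.** The missing-data rule is one sentence under Statistical Analyses, Samples, directly after the per protocol set is defined: "Mean value in Placebo group for the relevant day will be used to fill lacking/missing data". This document gives no missing-data assumption, variance correction or sensitivity analysis to go with it.

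The endpoints it might apply to are of three kinds:

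- **Primary (footnote 1), one value per child:** "Diarrhea duration is considered as the time between receiving the first dose of investigational medicine /placebo and the normal consistency of stool pattern".
- **By-day score (secondary endpoint 4):** "Total CDS score at 24, 48, and 72 hours after treatment initiation".
- **Yes/no outcomes (for example secondary endpoint 1):** "Percentage of patients without diarrhea following 48, 72, and 96 hours of treatment".

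The analysis sets limit who can be filled. The Full Analysis Set, which carries the intention-to-treat efficacy analysis, leaves out children for "lack of any data of the patient following randomization" and for "withdrawal of a patient due to early discharge" with persisting symptoms. The per protocol set admits no missing visits.

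On follow-up, the schedule places "Return of patient diary" on Day 6. The Day 10 contact is meant "to interview the parents/adopters about the patient's health, presence of any complications, and use of medications".

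**The concern.** Read plainly, a sentence with no arm limit fills Ergoferon children with the Placebo mean. That pulls the arms together wherever Ergoferon data are missing. The filled constant is then analysed as if it had been observed, so the standard error does not reflect how little is known. The intention-to-treat estimate and test would depend on which arm has the gaps as well as on the treatment effect.

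The rule also does not fit most endpoints. A duration belongs to no particular day, and the document does not say how a by-day fill becomes a duration. A missing yes/no cannot take a group mean without becoming a fraction.

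The scoring of unresolved diarrhea is a separate gap. Footnote 1 defines duration only by reaching normal stool, so a child still ill when the diary is returned has no defined value. These are the longest illnesses, and different analysts could score them differently.

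**Working it through.** **Inputs.** Difference 12 h, SD 36 h (Assumptions about the expected effects); two-sided 5%, power 80% (items 1.1–1.3); 143 per group at the final analysis; Placebo mean 2.9 days × 24 = 69.6 h (footnote 11), so the Ergoferon mean is taken as 69.6 − 12 = 57.6 h. Missing fractions are assumptions. The tests below are single-look at 5%.

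**Plan's own figure.** n per group = 2 × 36² × (1.960 + 0.842)² / 12² = 141.3. The two-look O'Brien-Fleming inflation of 1.0078 gives 142.4, hence 143, and half of that, 71.2, gives 72 at interim. The stated sizes reproduce and are not in dispute.

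**Fill applied to durations, random missingness.** Let d1 and d2 be the fractions missing in Ergoferon and Placebo.

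*Estimate.* Filled Placebo mean = observed Placebo mean. Filled Ergoferon mean = (1 − d1) × observed Ergoferon mean + d1 × observed Placebo mean. The filled difference is therefore (1 − d1) × observed difference:

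| d1 | 12 × (1 − d1) |
|---|---|
| 5% | 11.4 h |
| 10% | 10.8 h |
| 20% | 9.6 h |

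With d1 = 0 the difference is unbiased, whatever d2 is. The same algebra holds for the dehydration score.

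*Type I error.* True variance / variance used by the t-test ≈ (1 − d1)/(1 − d2). Actual type I error ≈ 2 × [1 − Φ(1.96 × √((1 − d2)/(1 − d1)))].

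| Ergoferon / Placebo missing | Formula | Simulation |
|---|---|---|
| 0 / 2% | 0.052 | 0.054 |
| 0 / 5% | 0.056 | 0.057 |
| 0 / 10% | 0.063 | 0.064 |
| 0 / 20% | 0.080 | 0.081 |
| 10 / 20% | 0.065 | 0.062 |
| 20 / 20% | 0.050 | 0.049 |
| 20 / 10% | 0.038 | 0.037 |

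The simulations used 20,000 or 40,000 trials per setting; the 40,000-trial run gave 0.051 with nothing missing.

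*Coverage, equal missingness f, true 12 h.* Here the two variances nearly agree, and the loss comes from the bias 12f.

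- f = 10%: bias 1.2 h; standard error of the filled difference √(2 × 1296 × 0.9 / 143) = 4.04 h; coverage about 0.94.
- f = 20%: bias 2.4 h; standard error √(2 × 1296 × 0.8 / 143) = 3.81 h; coverage about 0.905 (simulated 0.904).

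**Unresolved diarrhea, only if such children were treated as missing and filled.** Durations are assumed lognormal or gamma with means 57.6 and 69.6 h and SD 36 h. The fill is the mean of the resolved Placebo children.

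| Cut | Unresolved, Ergoferon | Unresolved, Placebo | Fill | Difference after fill |
|---|---|---|---|---|
| 120 h | 5.9–6.3% | 8.7–9.3% | 61.7 h | 9.5–9.7 h |
| 144 h | 2.7–3.0% | 3.9–4.1% | 64.9–65.5 h | 10.8–10.9 h |

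A child with at least 120 h of diarrhea would thus be scored at about 62 h.

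**The case against.** The strongest defence concerns reach. The trial is sized on per protocol completers, who have no missing visits. The Full Analysis Set already drops children with no data and symptomatic early discharges. Children are seen daily in hospital and the pediatrician checks the diary. Few values may be filled, and at 2–5% missing little changes. All of this stands, and it limits the severity. It does not remove the point: children with partial data, or still ill on Day 6, remain in the intention-to-treat analysis.

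The wording about the relevant day also suggests that the rule was meant for by-day variables. That is the closer fit, and every duration figure above depends on the wider reading. Under the narrow reading the defect for the primary endpoint is an omission, while the shrinkage still applies to the dehydration score.

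A reader might infer that the rule always biases the result or always inflates type I error. It does neither. Placebo-only random missingness leaves the difference unbiased. Inflation under random missingness needs more missing in Placebo than in Ergoferon, and the reverse makes the test conservative.

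Nor is the fill always worse than using observed cases. Assume no true effect and long durations lost more often (gamma durations, mean 69.6 h, SD 36 h, losses from the upper half). With 15% Ergoferon and 5% Placebo missing, the fill rejects in 8.7% of trials and observed cases in 10.9%; at 20% and 10% missing, the figures are 10.2% and 12.8%. Neither approach repairs outcome-dependent loss.

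Finally, the document calls itself a protocol summary, so the missing scoring rule is a statement about this document only. The Day 10 interview may give some information on later resolution.

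**Conclusion.** The concern holds in conditional form and should be fixed. The rule has no stated scope, cannot serve the percentage endpoints, and either leaves a missing primary outcome without a rule or fills it with the Placebo mean. In the second case, under random missingness, the 12 h effect shrinks in proportion to the Ergoferon fraction missing. Type I error exceeds the limit in item 1.2 when Placebo has more missing, reaching about 0.064 at 10% and 0.08 at 20% Placebo-only. With equal fractions the test holds its level while coverage drops to about 0.94 at 10% and 0.90 at 20%. These sizes rest on assumed fractions, 143 per group, SD 36 h and a single-look test.

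The lack of a rule for unresolved diarrhea is a separate gap in this document. The fall to 9.5–9.7 h also requires that such children count as missing, which is an inference. A reader might go further and infer a near-vanishing effect by combining the 12 h difference with footnote 11's SDs of 1.2 and 1.8 days. The documents do not support that: those SDs belong to means of 1.9 and 2.9 days, a 24 h difference, so the combination mixes two sources.

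**What to change.** - Remove the placebo-mean fill from the main efficacy analyses; keep it at most as a labelled sensitivity analysis.
- For missing durations in the Full Analysis Set, use multiple imputation within arm. This keeps the mean-difference hypotheses of item 1.5 and carries the uncertainty into the standard error.
- State that unresolved diarrhea is right-censored at the last stool record and not filled, so that any imputed duration must exceed that time. State whether the Day 10 interview may be used to date later resolution.
- Add a supportive time-to-resolution analysis with LIFETEST, which is already listed.
- For the dehydration score, use the already listed mixed model on observed data.
- For the diarrhea and recovery percentages, count a child without documented resolution as not resolved.
- Add a sensitivity analysis that treats withdrawn children as unresolved to the end of diary follow-up, because neither imputation nor censoring repairs outcome-dependent missingness.

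The cost is SAP wording and programming, plus slightly wider intervals. No new data are needed. The choices should be fixed before unblinding.

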 - b. assumption on expected effects declared in the main efficacy criterion of the protocol.
- 1.8 calculation of sample size of groups 1 and 2 for two-sided test for interim and final analysis will be made using the formula:

$$N_1=N_2=(\sigma_1^2+\sigma_2^2)I$$

where N_1 and N_2 are sample sizes in Ergoferon and Placebo groups;

 σ_1 and σ_2 are expected standard deviations in groups 1 and 2;

I – Fisher's information determined using the formula:

$$I=(F^{-1}(1-\alpha)+F^{-1}(1-\beta))^2/\theta^2$$
,

CONFIDENTIAL Page 11 of 14

where $F^{-1}(1-\alpha)$ and $F^{-1}(1-\beta)$ are tabular values of z-test for α and β , a $\theta = (m_1-m_2)$.

1.9 final sample size will be determined using the formula:

$$N_F = N_{PP}/(1-C_w)$$
,

where N_F – final sample size;

N_{PP} – result of calculation in cl. 1.8, i.e. scheduled number of subjects completing the study per protocol;

 C_W – withdrawal coefficient.

2. Assumptions about the expected effects of the clinical study.

Given that the results of the previous studies, the difference between Ergoferon effect consisting in reduced mean diarrhea duration and Placebo effect is expected to be at least 12 hours in favour of Ergoferon with group standard deviation of at least 36 hours¹¹.

According to the statistical considerations and assumptions above, each group size will be:

- a) at interim analysis 72 subjects;
- b) at final analysis 143 subjects.

Hence, full PP analysis set will included 286 patients.

Given potential negative results of PCR diagnosis, screening failures and further withdrawals for various reasons it was decided to double the sample (C_w =50%) and and enroll at least 572 subjects (286 per group).

Statistical criteria

All the statistical calculations will be performed using two groups of statistical criteria:

- parametric to evaluate continuous and interval random variables;
- non-parametric for:
 - assessments of equality / inequality in the proportion of patients when compared for different visits,
 - analysis of frequencies of the compared features,
 - assessment of continuous and interval random variables in case of violation of the normality assumption.

The following SAS procedures are supposed to be used for interim analysis:

- SEQDESIGN, SEQTEST design and performance of interim analysis.
- Conditions for early study termination will be established using O'Brien-Fleming stopping boundary.

Parametric criteria

CONFIDENTIAL Page 12 of 14

11

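### The interim look may change the sample size, and the O'Brien-Fleming boundary alone does not guarantee a type I error below 5% if that change depends on the observed treatment difference

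*Combined protocol and SAP*

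**What the plan says.** Under Evaluation of sample size, clause 1.6 gives the interim analysis its purpose: "to assure potential adjustment of sample size or terminate the study due to inadequate efficacy/high efficacy". Sub-item (a) adds that "calculations will be made using O'Brien-Fleming boundary", and sub-item (b) sets the information fractions at 0.5 and 1.0. Under Statistical criteria, the interim tools are "SEQDESIGN, SEQTEST design and performance of interim analysis", followed by "Conditions for early study termination will be established using O'Brien-Fleming stopping boundary".

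The error requirement is in clauses 1.2 and 1.3: the type I error probability "is allowed to be less than 5" per cent, and "the statistical criteria are 2-sided". The interim uses 72 patients per group and the final analysis 143 per group.

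The documents do not say how the sample size would be adjusted, in which direction, up to what maximum, or from blinded or unblinded data. They also do not say how the final test would be formed after a change. The multiplicity corrections under Parametric criteria concern comparisons between groups, not this adaptation.

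**The concern.** Stopping for high or low efficacy requires the between-group difference, and the adjustment belongs to the same clause and the same look. Whoever adjusts N may therefore know the interim effect. An O'Brien-Fleming boundary is derived for stage sizes that do not depend on that effect. If a weak interim result leads to a larger second stage and the pooled statistic is still compared with the planned critical value, the chance of a false positive can exceed the nominal level. The test affected is the one on the primary endpoint, diarrhea duration.

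**Working it through.** **Inputs from the plan.** Difference and SD: "is expected to be at least 12 hours in favour of Ergoferon with group standard deviation of at least 36 hours". Power "is assumed to be 80" per cent; two-sided 5%; looks at 72 and 143 per group.

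**Inputs assumed.** The plan gives no maximum N and no adjustment rule. Caps of 1.5, 2, 3, 5 and 10 times 143 per group are used to show the range.

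**Step 1: reproduce the plan's figure.**
- Fixed design: n = 2 × 36² × (1.960 + 0.842)² / 12² = 141.3, so 142 per group.
- Two-look O'Brien-Fleming at information 0.5 and 1.0, two-sided 5%: reject if |Z| ≥ 2.797 at the interim or |Z| ≥ 1.977 at the end (2.797 ≈ 1.977 × √2).
- Power with these boundaries is 79.9% at 142 and 80.2% at 143 per group. So 143 is the smallest size that reaches 80%. Half of it, rounded up, is 72. The plan's numbers are reproduced exactly.

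**Step 2: type I error with no change of N.** It is 5.0%. The boundary works as designed.

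**Step 3: type I error when N depends on the interim effect.** Let z₁ be the interim statistic, Z₂ the statistic from second-stage patients only, and n ≥ 143 the new size per group. The ordinary final statistic is

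Z = [√72 · z₁ + √(n − 72) · Z₂] / √n, compared with 1.977.

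Conditional power at the observed trend is

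CP(n) = 1 − Φ{ [1.977√n − √72 · z₁] / √(n − 72) − z₁√(n − 72) / √72 }.

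The rule raises n until CP(n) reaches 80% or the cap is met. The conditional-power figures come from 4 million simulated null trials per scenario. The worst case picks, at each z₁, the n within the cap that maximises the rejection probability, and integrates over z₁.

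| Two-sided type I error | 1.5× | 2× | 3× | 5× | 10× |
|---|---|---|---|---|---|
| Raised only if the drug is ahead | 5.3% | 5.5% | 5.7% | 5.9% | – |
| Raised in either direction | 5.7% | 6.0% | 6.4% | 6.8% | – |
| Worst case over all increase rules | 5.8% | 6.2% | 6.6% | 6.9% | 7.2% |
| Raised only if CP is 36% to 80% and the drug is ahead | 4.97% | 4.92% | 4.91% | – | – |

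**Step 4: does a recomputed boundary cure it?** SEQTEST can recompute the final boundary for a new information level. At a cap of 2×, keeping 2.797 and re-solving the final value gives about 1.99. The error falls from 6.0% to 5.9% (either direction) and from 5.5% to about 5.45% (drug ahead only). It stays above 5%, because the recalculation treats the new size as unrelated to the observed effect.

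**Step 5: fixed weights.** Replace Z by

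Z_w = √(72/143) · z₁ + √(71/143) · Z₂

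and keep 2.797 and 1.977. Under the null hypothesis Z₂ is standard normal whatever n is chosen, so Z_w keeps its planned distribution. Simulated error is 4.97% to 5.02% at caps of 1.5×, 2× and 3×, for every rule tried.

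**The case against.** The strongest reply is that clause 1.6 mentions only a possible adjustment and states no effect-driven rule. Clause 1.7 ties the calculation to the declared effect, and the formula in 1.8 uses the expected SDs. Re-running it with an updated SD and the declared 12 hours is a fair reading. So is a change in enrolment alone, since the 572 rests on an assumed 50% loss that includes negative PCR results. Neither need depend on the treatment difference. The file also calls itself a protocol summary, so details may exist elsewhere. This stands as far as it goes, but the formula in 1.8 also divides by the squared difference between groups, and nothing says that this input stays fixed or that the adjustment is blinded.

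A second reply is that the same clause foresees stopping for inadequate efficacy, which would remove many of the null trials in which N would be raised. This too has force. With increases only when the drug is ahead, and the trial always stopped below 5% conditional power (an assumed threshold), error in the favourable direction was 2.41% to 2.42% against a nominal 2.5%. The plan, however, gives no futility threshold and does not make such a stop binding.

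A reader might infer that the boundary fails, or that the error will be 6% to 7%. The documents do not support either. Several permitted adjustments cause no inflation. The figures of 6% and above come from worst-case choices or from rules that also raise N when placebo is ahead, which is hard to square with the direction of the alternative hypothesis in 1.5.

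**Conclusion.** The point holds as a gap in error control. Clause 1.6 permits a sample size change at a comparative look, and the only stated protection does not guarantee the rate required by 1.2 if the change depends on the observed difference. The most relevant size is about 5.3% to 5.9% (drug ahead only, caps 1.5× to 5×). Increases in either direction give 5.7% to 6.8%, and the worst case is 5.8% (1.5×) to 7.2% (10×). All these figures rest on assumed caps. All but the worst case also assume a conditional-power rule, and all use the ordinary pooled statistic with the unchanged final boundary. The inflation is moderate and avoidable. It would be too strong to call the plan wrong as written, because it names no faulty adjustment method; it leaves open adjustments that the boundary does not cover.

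**What to change.** Cheap improvement, to be written before the interim data are seen. Add to clause 1.6: if the sample size is changed after the comparative interim, the final test combines the stage-1 and stage-2 z-statistics with pre-fixed weights √(72/143) and √(71/143), and compares the result with the original boundaries of 2.797 and 1.977. The same clause should state the adjustment rule, the maximum N and who sees the unblinded results. If the primary analysis moves to the Mann-Whitney test or a generalized model, the stage-wise z-statistics should come from that same method.

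Alternatively, restrict the adjustment to a blinded re-estimate of the pooled SD.

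Cost: a few sentences. The planned 143 per group does not change. If N is not changed, the weighted and ordinary statistics are essentially the same. If N is changed, there is a small loss of efficiency, because second-stage patients no longer count in proportion to their number.
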